### 4.4 Reproductive Potential

The potential effects of ontamalimab on embryofetal or postnatal development have not been assessed in humans. Preliminary results from an enhanced pre-and postnatal development toxicity study of ontamalimab in nonhuman primates indicated that, at the dose levels tested (30 and 60 mg/kg), infant losses were increased in ontamalimab-exposed animals when compared both to control animals in the study and to the historical control animal data from the testing facility. The relevance of this finding to humans is unknown but cannot be excluded. Based on the exposure in the Phase 2 clinical study A7281009 (area under the concentration-time curve [AUC] from 0 to 672 hours [AUC0-672h] at 6140 µg·h/mL following repeated SC administration of 75 mg SHP647 Q4W), maternal exposure (AUC) in cynomolgus monkeys within a similar duration at 30 and 60 mg/kg once every 10 days is approximately 77 times and 172 times the clinical exposure, respectively.

To minimize the risk of unintentional exposure of the embryo or fetus in the clinical study, all sexually active male and female subjects who, in the opinion of the investigator, are biologically capable of having children and with their partners are at risk of pregnancy, must agree to use an appropriate form of contraception (ie, highly effective methods for female and medically

appropriate methods for male study subjects), in accordance with the package instructions/leaflet, for the duration of the active treatment period and for at least 16 weeks after the last dose of investigational product.

True abstinence is considered to be a highly effective contraception (ie, a method that results in a failure rate of <1% per year) when it is in line with the preferred and usual lifestyle of the subject. Periodic abstinence (eg, calendar, ovulation, symptothermal, postovulation methods), declaration of abstinence for the duration of exposure to investigational product, and withdrawal are not appropriate methods of contraception.

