During the induction studies (SHP647-301 and SHP647-302), the investigator or designee in consultation with the subject will confirm the subject's childbearing potential status. For subjects of childbearing potential, it must be confirmed and documented that the subject has selected the most appropriate method of contraception (ie, highly effective methods for female and medically appropriate methods for male study subjects) from the permitted list of contraception methods. Subjects must affirm the consistent and correct use of at least 1 of these selected methods. Regular contraception check discussions will take place at the time points specified in [Table 1](#) (ie, at each site visit) and will be documented. In addition, the subject must be instructed to call the site immediately if the selected contraception method is discontinued or if pregnancy is known or suspected.

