#### **4.4.1 Contraceptive Methods for Female Study Subjects**

At baseline (Visit 1) in this study, the childbearing potential of subjects must be re-established and documented if the subject's status has changed since the induction studies (SHP647-301 or SHP647-302) (see Section [7.3.3.7](#)).

Sexually active females of childbearing potential must already be using an established highly effective form of contraception, and must be advised to use appropriate contraceptives throughout the study period and for 16 weeks following the last dose of investigational product. If hormonal contraceptives are used they should be administered according to the package insert. Contraception methods with low user dependency should preferably be used, in particular when contraception is introduced as a result of participation in the clinical study. The following highly effective contraceptive methods are considered to be methods with low user dependency:

- Intrauterine device
- Intrauterine hormone-releasing system
- Bilateral tubal occlusion

- Male sterilization/vasectomized partner
- Implantable progesterone-only hormonal contraception associated with inhibition of ovulation.

Female subjects should be in 1 of the following categories:

- Postmenopausal (12 consecutive months of spontaneous amenorrhea and  $\geq 51$  years of age); postmenopausal status should be confirmed by follicle-stimulating hormone (FSH) testing.
- Surgically sterile (having undergone one of the following surgical acts: hysterectomy, bilateral tubal ligation, bilateral oophorectomy or bilateral salpingectomy) and at least 6 weeks poststerilization or has medically confirmed ovarian failure.
- Females of childbearing potential with a negative pregnancy test result at baseline (ie, Week 12 of the induction study SHP647-301 or SHP647-302; Week 0 of Study SHP647-303). Females of childbearing potential must agree to practice true abstinence (refrain from sexual activity that could result in pregnancy) or agree to use appropriate methods of highly effective contraception.

Highly effective contraception (ie, methods that result in a failure rate of  $<1\%$  per year when used consistently and correctly) are:

- Combined (estrogen- and progestogen-containing) hormonal contraceptives associated with inhibition of ovulation (oral, intravaginal, transdermal) stabilized for at least 30 days before baseline (ie, Week 12 of the induction study SHP647-301 or SHP647-302; Week 0 of Study SHP647-303)

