#### 4.4.2 Contraceptive Methods for Male Study Subjects

Contraception is required for all sexually active male subjects, who with their female sexual partners must agree to use one of the following appropriate methods of contraception throughout the study period and for 16 weeks following the last dose of investigational product.

Appropriate methods of contraception for male subjects are:

- Male condom with spermicide; however, if spermicide is not available in the country, additional contraception (ie, 1 of those listed below) must be used in addition to a male condom.
- Male sterilization with documented absence of sperm in the postvasectomy ejaculate.
  - Appropriate methods for female sexual partners of male subjects are (unless the female sexual partner is sterile [surgically or documented nonsurgical sterility]):
- Use of a highly effective method of contraception listed in Section 4.4.1 OR an acceptable method of contraception (failure rate of >1% per year)
  - Female condom with spermicide (use by female sexual partner); however, if spermicide is not available in the country, additional contraception (ie, 1 of those listed below) must be used in addition to a female condom
  - Intrauterine device with spermicide
  - Contraceptive sponge with spermicide
  - Intravaginal system (eg, vaginal ring with spermicide, a diaphragm with spermicide, or a cervical cap with spermicide).

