### 8.1.7 Pregnancy

All pregnancies are to be reported from the time informed consent is signed until the end of the defined safety follow-up period stated in Section 7.2.3.

Any report of pregnancy for any female study participant or the partner of a male study participant must be reported within 24 hours to the Shire Global Drug Safety Department using the Shire Investigational and Marketed Products Pregnancy Report Form. A copy of the Shire Investigational and Marketed Products Pregnancy Report Form (and any applicable follow-up reports) must also be sent to the CRO/Shire medical monitor using the details specified in the [emergency contact information](#) section of the protocol. The pregnant female study participant must be withdrawn from the study.

Every effort should be made to gather information regarding the pregnancy outcome and condition of the infant. It is the responsibility of the investigator to obtain this information within 30 calendar days after the initial notification and approximately 30 calendar days postpartum. If the pregnancy outcome is a live birth, the vital status and clinical condition of the infant should be obtained and documented at 1 year postpartum.

Pregnancy complications such as spontaneous abortion/miscarriage or congenital abnormality are considered SAEs and must be reported using the Shire “Clinical Study Serious Adverse Event and Nonserious AE as Required by the Protocol Form.” Note: An elective abortion is not considered an SAE.

In addition to the above, if the investigator determines that the pregnancy meets serious criteria, it must be reported as an SAE using the Shire “Clinical Study Serious Adverse Event and Nonserious AE as Required by the Protocol Form” as well as the Shire Investigational and Marketed Products Pregnancy Report Form. The test date of the first positive serum/urine  $\beta$ -hCG test or ultrasound result will determine the pregnancy onset date.

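### Under Amendment 3, the Section 8.1.7 pregnancy reporting period can end 28 − d days before required contraception does, for subjects not entering SHP647-304 whose ET visit is d < 28 days after the last dose

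*Protocol*

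**What the plan says.** **Reporting period.** Protocol Section 8.1.7 opens: "All pregnancies are to be reported from the time informed consent is signed until the end of the defined safety follow-up period", with a pointer to Section 7.2.3. Under Section 7.2.3 the last follow-up visit is 12 weeks ±10 days after the ET visit for early withdrawals, and Day 448 ±10 days for subjects who complete 52 weeks. Subjects who enter SHP647-304 have no follow-up here and are outside this point.

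**A second sentence without an end date.** The next paragraph of Section 8.1.7 says: "Any report of pregnancy for any female study participant or the partner of a male study participant must be reported within 24 hours".

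**Contraception period.** Section 4.4 requires contraception "for the duration of the active treatment period and for at least 16 weeks after the last dose of investigational product". Section 4.4.1 repeats this for women ("must be advised to use appropriate contraceptives throughout the study period and for 16 weeks following the last dose of investigational product") and Section 4.4.2 for men ("methods of contraception throughout the study period and for 16 weeks following the last dose of investigational product").

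**Active enquiry.** Section 4.4 ties the site's questions to scheduled visits: "Regular contraception check discussions will take place at the time points specified in" Table 1. It also tells subjects to call the site if they stop their contraceptive method or suspect pregnancy, with no end date.

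**Why the outcome is wanted.** For live births, Section 8.1.7 asks that "the vital status and clinical condition of the infant should be obtained and documented at 1 year postpartum".

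**The concern.** The two periods have different anchors. Reporting ends a fixed time after a visit, and contraception ends a fixed time after the last dose. They match only if the visit falls at one particular interval after that dose, and nothing in the protocol ties them together.

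Where the visit comes sooner, there are days on which the protocol still requires contraception but its defined reporting period has closed and no scheduled contact remains. The two sentences of Section 8.1.7 then leave it unclear whether a site must forward a pregnancy that a subject phones in: the first is dated and the second is not. At stake are a few pregnancy outcomes in a safety database. No efficacy analysis or error rate is involved.

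**Working it through.** **Inputs**

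- Contraception ends 16 × 7 = 112 days after the last dose (Sections 4.4, 4.4.1, 4.4.2).
- Follow-up ends 12 × 7 = 84 days after ET, ±10 days (Section 7.2.3).
- The last scheduled dose is at Week 48, Day 336. No dose is given at Week 52/ET, and treatment visits have a ±10-day window (Table 1).
- The half-life is 16 days (Summary of Changes, Amendment 3).
- d is the number of days from last dose to ET. The documents do not give its distribution, so 0 to 28 is an assumed range.

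**The plan's own figure.** Week 52 is Day 364, and 364 + 84 = 448, which reproduces Visit 15. Measured from the last dose, 448 − 336 = 112 days, so the nominal completer schedule is exactly aligned with contraception.

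**Schedule before Amendment 3.** SAP Appendix 16.1 has 16 weeks of follow-up, ending at Day 476 (364 + 112). Reporting would then end at d + 112 days after the last dose. Nominally that covers the contraception period for every d ≥ 0, so the mismatch belongs to the 12-week follow-up.

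**Early withdrawals.** Reporting ends d + 84 days after the last dose:

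- nominal gap = 112 − (d + 84) = 28 − d
- visit at the early edge (−10 days): 38 − d
- visit at the late edge (+10 days): 18 − d

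Negative values mean no gap.

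| d (days) | Nominal gap | Early edge | Late edge |
|---|---|---|---|
| 7 | 21 | 31 | 11 |
| 14 | 14 | 24 | 4 |
| 18 | 10 | 20 | 0 |
| 21 | 7 | 17 | 0 |
| 28 | 0 | 10 | 0 |
| 38 | 0 | 0 | 0 |

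At d = 0 the nominal gap would be 28 days, but this is a theoretical limit only.

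**Can d be below 28?** Section 4.5 requires the ET evaluations at any discontinuation. The 2-week minimum in Section 7.2.2.2 covers only subjects entering SHP647-304. The Amendment 3 rule, no later than 4 weeks (±10 days) after the last study visit before SHP647-304 Amendment 4, is a ceiling. So no floor is stated for the subjects concerned here.

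**Completers.** Gap = (last-dose day + 112) − Visit 15 day:

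- 336 + 112 − 448 = 0
- 346 + 112 − 448 = 10
- 336 + 112 − 438 = 10
- 346 + 112 − 438 = 20 (late dose and early final visit together)

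**Residual drug when follow-up ends.** This assumes first-order elimination and applies only where the last maintenance dose was ontamalimab. Fraction = 2^(−t/16):

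- d = 14, t = 98: 1.43%
- d = 0 limit, t = 84: 2.63%
- end of contraception, t = 112: 0.78%

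**The case against.** **Few subjects are exposed to the gap.** The 12-week follow-up exists only under Amendment 3. There the ET visit replaces the next four-weekly visit, so d near 28 is the natural case. Treatment failure needs one to two weeks of sustained worsening plus endoscopy (Section 4.5.1.1), so d near 0 is unlikely. Withdrawals under the earlier 16-week follow-up are not affected on nominal timing. All of this stands and narrows the point. It does not supply a minimum interval.

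**The value d = 14 has no source for this group.** This is correct. The protocol's only 2-week figure concerns subjects who roll over, who are excluded here. The value is illustrative.

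**Many have no ontamalimab in their last dose.** This is also correct. By the planned allocation, (148 + 148 + 104/5)/696, about 46%, are on maintenance placebo. Subjects on placebo in both studies cannot enter SHP647-304, so they fall into this follow-up group with no drug exposure at all. The residual percentages do not apply to placebo subjects.

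**The two periods need not match.** One is a precaution and the other is data collection, and no section says they must be equal. The undated 24-hour sentence, the instruction to call the site, and reporting of related SAEs after the study (Section 8.2.4) all remain. These are real but partial safeguards. The first sits beside a dated sentence that a site could read as controlling, the second relies on the subject, and the third does not cover an uncomplicated pregnancy.

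**A stronger reading to avoid.** A reader might infer that pregnancies in these days go unreported, or that fetuses are exposed to a meaningful dose. The documents support neither. The 24-hour sentence may well capture a pregnancy that is phoned in. Residual drug is low, and the primate infant losses occurred at "approximately 77 times and 172 times the clinical exposure".

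**Conclusion.** The mismatch is real and small. Under Amendment 3, for subjects followed up in this study with d < 28, the defined reporting period nominally ends 28 − d days before required contraception does. Completers have no nominal gap. A shift at one visit window can open about 10 days, and 20 days needs opposite edges to combine.

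What clearly stops early is the defined period and the site's active enquiry. Whether a late pregnancy that reaches the site must be forwarded is ambiguous. The result rests on the dated sentence in Section 8.1.7 meaning what it says and on some subjects having d < 28. The documents show neither how many there are nor how d is distributed, and the number may be very small. This is a minor safety-reporting improvement, and no efficacy conclusion depends on it.

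**What to change.** In Section 8.1.7, have pregnancies reported until the later of the end of safety follow-up and 16 weeks after the last dose of investigational product. This makes the gap zero for every d and every visit-window shift, and it settles the ambiguity between the two sentences.

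Where the final visit falls before 16 weeks after the last dose, add one telephone contact at or shortly after 16 weeks to ask about pregnancy and contraception. Allowing it to fall shortly after leaves room for a recent conception to be recognised. Subjects who have withdrawn consent would not be called (Section 4.5.1).

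The cost is a one-sentence protocol change with the usual IRB/EC approval (Section 10.3.2), in a closing study with about 164 sites in about 31 countries, plus one call for a small subset. That subset is subjects of reproductive potential, or with a partner of childbearing potential, who do not enter SHP647-304 and whose final visit comes too soon. The sentence has value even if the call is judged not worth adding.

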### 8.1.8 Abuse, Misuse, Overdose, and Medication Error

Abuse, misuse, overdose, or medication error (as defined below) must be reported to the sponsor according to the SAE reporting procedure whether or not they result in an AE/SAE as described in Section 8.2. Note: The 24-hour reporting requirement for SAEs does not apply to reports of abuse, misuse, overdose, or medication errors unless these result in an SAE.

The categories below are not mutually exclusive; the event can meet more than 1 category.

- **Abuse** – Persistent or sporadic intentional intake of investigational product when used for a nonmedical purpose (eg, to alter one’s state of consciousness or get high) in a manner that may be detrimental to the individual and/or society
- **Misuse** – Intentional use of investigational product other than as directed or indicated at any dose (Note: this includes a situation where the investigational product is not used as directed at the dose prescribed by the protocol)
- **Overdose** – Intentional or unintentional administration of investigational product at a dose interval that is less than 2 weeks between doses
- **Medication Error** – An error made in prescribing, dispensing, administration, and/or use of an investigational product. For studies, medication errors are reportable to the sponsor only as defined below.

Cases of subjects missing doses of the investigational product are not considered reportable as medication errors.

Medication errors should be collected/reported for all products under investigation.

The administration and/or use of the unassigned treatment is/are always reportable as a medication error.

The administration and/or use of an expired investigational product should be considered as a reportable medication error.

There is no specific antidote for overdose with ontamalimab. Treatment should be symptomatic and supportive.

### **8.1.9 Unexpected Adverse Event**

An unexpected AE is an AE whose nature, severity, specificity, or outcome is not consistent with the term, representation, or description used in the reference safety information (RSI).

“Unexpected” also refers to the AEs that are mentioned in the IB as occurring with a class of drugs or as anticipated from the pharmacological properties of the product, but are not specifically mentioned as occurring with the particular product under investigation.

The expectedness of AEs will be determined by the sponsor using the IB as the RSI. This determination will include considerations such as the number of AEs previously observed, but not on the basis of what might be anticipated from the pharmacological properties of a product.

### **8.1.10 Suspected Unexpected Serious Adverse Reaction**

A suspected unexpected serious adverse reaction (SUSAR) is defined as any suspected adverse reaction to study treatment (ie, including active comparators) that is both serious and unexpected.

The event(s) must meet all of the following:

- Suspected adverse reaction
- Serious
- Unexpected
- Assessed as related to study treatment.

## **8.2 Serious Adverse Event Procedures**

### **8.2.1 Reference Safety Information**

The reference for safety information for this study is Section 6.8 of the ontamalimab IB, which the sponsor has provided under separate cover to all investigators.

### **8.2.2 Reporting Procedures**

All initial and follow-up SAE reports must be reported by the investigator to the Shire Global Drug Safety Department and the CRO/Shire medical monitor within 24 hours of the first awareness of the event. Note: The 24-hour reporting requirement for SAEs does not apply to reports of abuse, misuse, overdose, or medication errors (see Section 8.1.8) unless they result in an SAE.

The investigator must complete, sign, and date the Shire “Clinical Study Serious Adverse Event and Nonserious AE as Required by the Protocol Form” and verify the accuracy of the information recorded on the form with the corresponding source documents (Note: Source documents are not to be sent unless requested) and fax or email the form to the Shire Global Drug Safety Department. A copy of the Shire “Clinical Study Serious Adverse Event and Nonserious AE as Required by the Protocol Form” (and any applicable follow-up reports) must also be sent to the CRO/Shire medical monitor using the details specified in the [emergency contact information](#) section of the protocol.

### 8.2.3 Serious Adverse Event Definition

An SAE is any untoward medical occurrence (whether considered to be related to investigational product or not) that at any dose:

- Results in death.
- Is life-threatening.  
Note: The term “life-threatening” in the definition of “serious” refers to an event in which the subject was at risk of death at the time of the event; it does not refer to an event which hypothetically might have caused death if it was more severe.
- Requires inpatient hospitalization or prolongation of existing hospitalization.  
Note: Hospitalizations, which are the result of elective or previously scheduled surgery for pre-existing conditions, which have not worsened after initiation of treatment, should not be classified as SAEs. For example, an admission for a previously scheduled ventral hernia repair would not be classified as an SAE; however, complication(s) resulting from a hospitalization for an elective or previously scheduled surgery that meet(s) serious criteria must be reported as SAE(s).
- Results in persistent or significant disability/incapacity.
- Is a congenital abnormality/birth defect.
- Is an important medical event.  
Note: Important medical events that may not result in death, be life-threatening, or require hospitalization may be considered an SAE when, based upon appropriate medical judgment, they may jeopardize the subject and may require medical or surgical intervention to prevent 1 of the outcomes listed in this definition. Examples of such medical events include allergic bronchospasm requiring intensive treatment in an emergency department or at home; blood dyscrasias or convulsions that do not

result in inpatient hospitalization; or the development of drug dependency or drug abuse.

#### **8.2.4 Serious Adverse Event Collection Time Frame**

All SAEs (regardless of relationship to study) are collected from the time the subject signs the informed consent until the defined safety follow-up period stated in Section 7.2.3 and must be reported to the Shire Global Drug Safety Department and the CRO/Shire medical monitor within 24 hours of the first awareness of the event.

In addition, any SAE(s) considered “related” to the investigational product and discovered by the investigator at any interval after the study has completed must be reported to the Shire Global Drug Safety Department within 24 hours of the first awareness of the event.

